4.0 STUDY ENDPOINTS AND SUBJECT POPULATION

4.1 Primary Endpoints

Primary Effectiveness Endpoint (Performance):

Technical Success, defined as the ability of the EndoRotor device to resect recurrent flat or sessile colorectal lesions without concomitant use of other resection modalities for mucosectomy and no definitely or probably device-related serious adverse events (SAEs) throughout the 90-day follow-up period.

Primary Safety Endpoint:

Assessment of Serious Adverse Events (incidence, relationship to device and severity) at index procedure and at 90 days, post-procedure.

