5.7 Index Procedure

All patients will receive the EndoRotor® treatment following the technique described by Interscope's Instructions for Use.

The mucosal resections are performed during standard flexible colonoscopy procedures. All medications given, pre- and post-procedure precautions and follow-up assessments are part of routine standard of care. This protocol concerns itself with the actual removal of the mucosal lesion once the abnormal area is identified using the colonoscope.

- Patients will be prepped in the usual manner for lower GI endoscopy prior to their interventional visit.
- The procedures will be performed with either Propofol sedation or under general anesthesia.
- When a mucosal lesion is found, the EndoRotor® system will be prepared by attaching the EndoRotor® catheter, foot pedal and the calibrated suction to the Control Unit, ensuring there is a filter in the collection unit (specimen trap), and then priming the catheter with 0.9% normal saline.
- Lesions will be injected using saline solution with dye such as Indigo carmine or Methylene Blue. Indelible ink (such as SPOT) will be injected into the region of the resection to identify the site after resection.
- The EndoRotor® catheter will be inserted through the working channel of the endoscope until it is in proper cutting position with the cutting surface oriented towards the mucosal lesion and the catheter no more than 3cm out of the scope. The physician will turn the motor on by depressing the blue pedal and engage cutting by holding the orange pedal for as long as he/she wishes to cut tissue.
- Cutting should be performed while moving the EndoRotor® catheter. The endoscopist will take care to not keep the suction activated when he/she is not intending to cut mucosa and when stopped for more than 1 second while apposed to tissue to not risk creating a perforation.
- Various techniques can be used to remove the lesion. Recurrent, flat or sessile lesions will be attempted to be removed entirely with the EndoRotor® with no other treatment modalities. The physician will utilize the recommended technique appropriate to the lesion until there is no longer visible evidence of mucosal lesion. The intent of the protocol is to complete lesion resection using the EndoRotor as the only treatment modality. However, should it prove not feasible to complete the resection with the EndoRotor, the investigator may convert to the use of an alternative resection modality.

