- For synchronous lesion interventions, respective lesion specimens should be isolated and separately collected to avoid confounding results.
- APC or similar techniques used for hemostasis on a resected lesion is not considered an alternative resection modality.
- Treat with EndoRotor, assess percentage of tissue removed with EndoRotor followed by photograph from region at equidistant location.
- Photo-document the region following EndoRotor treatment.
- If the complete lesion cannot be removed in a single treatment visit, a second visit can be scheduled to complete the removal in advance of the 90 day visit.

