7.0 RISK/BENEFIT ASSESSMENT

The Interscope EndoRotor® System has been cleared under the Pre-Market program as a 510(K) and certified with the CE Mark and is approved for commercial use wherever the CE Mark is recognized. The device's safety and performance have been established through extensive design verification and validation testing, including prior human use, and through a detailed risk analysis process per 21 CFR Part 803. Interscope does not anticipate new risks to be identified through this clinical study. A summary of the benefits and risks identified are provided below.

The main complications found to be associated with polypectomy appear to be bleeding/hemorrhage, perforation, and post-polypectomy syndrome, which are reported to occur in 0-10.8%, 0-2.3%, and 0.14-3.7% of patients, respectively. Deaths have been reported in only 2 studies, at a rate of 0.01% and 0.1%. The greatest risk factor for an adverse event is associated with increasing polyp size.

The EndoRotor® holds the promise to improve the resection of mucosal-based lesions in the GI tract (stomach, small and large intestines) by making the resections more precise, quicker and more comprehensive. Because of its design, the EndoRotor® suctions in mucosa and then cuts it (about 1750 times a minute) to quickly remove mucosal disease. This quick cutting action allows the user to precisely define the resection margins, allowing all gross visible disease to be removed. User errors tend to increase when fatigue increases. Reducing the procedure time from an hour to several minutes can help to reduce the fatigue associated with mucosal resections. There is the potential that we could see a reduction in persistent lesions (meaning better initial comprehensive removal of disease) when the EndoRotor® is used as the resection tool, meaning that in the future the necessity for second-look procedures could be reduced or eliminated, further decreasing patient morbidity. Because the EndoRotor® was engineered to be a simple device (it only resects mucosa), most users feel comfortable after a few attempts, narrowing the performance gap between an expert endoscopic proceduralist and one who is still in training. The ease with which physicians learn to use the EndoRotor® could also result in less patient morbidity.

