- ⁶ Pregnancy test for female subjects of child bearing potential within 1 day of procedure.
- ⁷ Second procedure can be completed if complete resection was not achieved during initial procedure

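### After an incomplete EndoRotor resection, the operator's choice to convert or to schedule a second session decides who enters the primary analysis, and the results mix lesions treated once and twice

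*Combined protocol and SAP*

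**What the plan says.** Section 5.7 gives two routes when the EndoRotor has not cleared the lesion at the index session. The first is conversion: "should it prove not feasible to complete the resection with the EndoRotor, the investigator may convert to the use of an alternative resection modality". The second is staging: "If the complete lesion cannot be removed in a single treatment visit, a second visit can be scheduled to complete the removal". Appendix 1, footnote 7, repeats the second route: "Second procedure can be completed if complete resection was not achieved during initial procedure". Neither route has an operational criterion, and the staging text does not name the modality to be used at the later visit.

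Technical Success in section 4.1 has two parts. The device must "resect recurrent flat or sessile colorectal lesions without concomitant use of other resection modalities for mucosectomy", and there must be "no definitely or probably device-related serious adverse events (SAEs) throughout the 90-day follow-up period". Neither section 4.1 nor section 8.4 limits the number of sessions.

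Section 8.2 puts the effectiveness analyses on the Per Protocol (PP) set. That set admits only subjects whose lesion was fully removed by the EndoRotor alone, who had no eligibility deviation and who attended the 90-day visit. The Intent to Treat (ITT) set holds everyone in whom the device resected any part of a lesion, with or without another modality. Section 8.4 also says that the analysis concerns the proportion of lesions in which disease persists. Section 8.7 pools sites without testing for differences.

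**The concern.** Two subjects can have the same device result at the index session, a lesion only partly removed, and still be classified differently because one operator converted and the other rebooked. The operator is unblinded and no rule guides the scoring. A converted subject does not meet the Technical Success definition and is not in PP. A subject staged and cleared by EndoRotor alone is in PP and meets the definition unless a device-related serious adverse event occurs.

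Two things are at stake. First, the composition of the primary analysis depends on local habit: a site that tends to stage keeps its harder lesions in PP, while a site that tends to convert loses them. Pooling without a site comparison would not reveal this. Second, single-session and staged lesions go into the same success and 90-day persistence figures after different amounts of treatment, and no planned table separates them.

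**Working it through.** **1. The plan's own figure.** Section 8.8 uses n = 60 and a success rate of 0.85, so x = 51. The Clopper-Pearson limits are the 0.025 quantile of Beta(51, 10) and the 0.975 quantile of Beta(52, 9), which give 0.734 to 0.929 with half-width 0.0974. The printed half-width, 0.0972, is reproduced to within rounding. The printed interval, 0.782 to 0.967, is not. That mismatch is a separate matter and does not affect this point. The 0.10 precision target is used below only as a yardstick.

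**2. The definitions side by side**, for a lesion incomplete after the index session:

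| Route taken | Technical Success wording (4.1) | PP set (8.2) | ITT set (8.2) |
|---|---|---|---|
| Converted to another modality | Not met | Excluded | Included |
| Staged, cleared by EndoRotor alone | Met, absent a device-related SAE | Included, if other PP conditions hold | Included |
| Staged, another modality at second visit | Unclear: only concomitant use is barred | Excluded | Included |

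The second row is inferred from the absence of a session limit. No section states it.

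**3. Size.** Assumptions: 60 treated subjects, one lesion each, no device-related SAE, full follow-up and no eligibility deviation. Let k be the number of lesions incomplete after session one. Of these, s are staged and cleared by EndoRotor alone, and k − s are converted. The documents give neither k nor s.

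- All treated subjects: rate = (60 − k + s)/60. Moving from s = 0 to s = k shifts it by k/60.
- PP: rate = (60 − k + s)/(60 − k + s) = 1, whatever s is.
- Cleared in one session, all treated: (60 − k)/60, whatever s is.

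| k | All converted (exact 95% CI) | All staged (exact 95% CI) | Shift |
|---|---|---|---|
| 3 | 57/60 = 0.950 (0.861 to 0.990) | 60/60 = 1.000 (0.940 to 1.000) | 0.05 |
| 6 | 54/60 = 0.900 (0.795 to 0.962) | 60/60 = 1.000 (0.940 to 1.000) | 0.10 |
| 9 | 51/60 = 0.850 (0.734 to 0.929) | 60/60 = 1.000 (0.940 to 1.000) | 0.15 |
| 15 | 45/60 = 0.750 (0.621 to 0.853) | 60/60 = 1.000 (0.940 to 1.000) | 0.25 |

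A mixed case falls between: k = 9 and s = 4 gives 55/60 = 0.917 (0.816 to 0.972). The shift reaches the 0.10 target at k = 6.

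In PP with k = 9, the result is 51/51 if all are converted (lower limit 0.930) and 60/60 if all are staged (lower limit 0.940). The rate is 1.000 in both; only the denominator moves.

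**4. Persistence.** With k = 9 and all staged, 9/60 = 15% of the lesions in the PP persistence figure have been treated twice. With all converted, it is 0/51, and the nine difficult lesions do not appear.

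**The case against.** The strongest reply is that the primary analysis is on PP. A reader might infer that conversion counts as a failure there, so that sites which stage would show a higher primary success rate. The documents do not support this: PP removes converted subjects, and the resection component is 100% under either route. This part of the reply stands in full.

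A reader might also infer that the operator's choice sets the primary endpoint. That is too strong. The choice arises only for lesions incomplete after session one, and the SAE component also decides the outcome. The two routes are also worded differently: one turns on whether completion with the device is feasible, the other on whether one visit is enough. That stands as wording, but nothing says how to tell the two situations apart.

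The word concomitant in section 4.1 might seem to let another modality at the second visit pass as a success. In PP it cannot, because such a subject is excluded. The ambiguity matters only for a result on all treated subjects.

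Section 7.0 says that "in the future the necessity for second-look procedures could be reduced or eliminated". A reader might conclude that the study fails to support a claim it makes. That text is background speculation, and second-look procedures are neither an objective nor an endpoint.

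Finally, allowing staged completion is a legitimate definition in a primarily descriptive study with no performance goal. Section 5.7 records the percentage removed, with photographs, and section 5.7.1 records whether the device achieved the attempted resection. This is a fair argument against making one-session success the only headline. With PP unchanged, that would also fail staged subjects while still excluding converted ones. It does not answer the need for a breakdown: the list in section 5.7.1 names neither the number of sessions nor the modality at each, and no analysis by session is planned.

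**Conclusion.** The point holds in a limited form. The plan offers two routes after an incomplete index resection and gives no rule for choosing between them or for scoring the second. The choice decides whether the subject enters the primary analysis, and the success and persistence figures combine lesions treated once and twice.

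The PP resection rate does not move. The effect appears among all treated subjects, as a shift of up to k/60: 5 points for k = 3 and 15 points for k = 9. These sizes rest on assumed values of k, on one lesion per subject, on no device-related SAE and on complete follow-up. The scoring of a two-session clearance as a success is inferred from silence. When to convert or stage is a clinical matter and is not judged here.

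**What to change.** Leave the clinical options as they are and settle the scoring and reporting.

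- In sections 4.1 and 8.4, report two rows on all treated subjects (the ITT set of section 8.2): (a) cleared by EndoRotor alone in one session; (b) cleared by EndoRotor alone in up to two sessions. Keep the SAE component in both.
- In both rows, count use of another resection modality at any session up to the 90-day visit as failure. This replaces reliance on the word concomitant. The existing statement in section 5.7 that hemostasis techniques are not resection modalities can stand.
- Record on the procedure CRF the number of sessions and the modality used at each.
- Show 90-day persistence by number of sessions.

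The resection component of row (a) does not depend on the convert-or-stage choice. The gap between (a) and (b) shows how much of the result came from second sessions.

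The cost is wording in two sections, one or two CRF fields, one or two table rows, and a reported rate that may be lower. No extra subjects or procedures are needed.

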3.2 Study Duration & Follow-Up

It is anticipated that the study will begin enrollment in June 2019. Enrollment is expected to continue until December 2019. Study subjects shall return for clinic visits in 90 days (+/- 14 days) post-procedure; data from these visits shall be collected. Primary and other endpoints will be assessed. All subjects will be treated per this protocol, the Instructions for Use, and as per standard of care, as indicated. The last follow-up visit is expected to be completed by March 2020 at the last subject's 90-day (+/- 14 days) follow-up visit. The study is complete following the collection of all study data and all final site visits have been completed in June 2020.

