4.2 Secondary Endpoints

The following is a list of other secondary endpoints to be explored:

- 1. Completeness, in percentage, of resection based on endoscopy film and/or photographs in addition to diagnostic assessment of specimen by the independent pathologist.
- 2. Presence of colon stenosis based on endoscopy film and/or photographs.
- 3. Rate of persistence of disease at the location of resection at 90 days.
- 4. Histologic assessment of the diagnostic value of the collected specimens.

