- 5. Results of the independent pathologist's assessment will be documented on the Histopathology Log within **30 days** of receiving the specimens and uploaded to the Sponsor's secure web server. The table will include site number, patient number, date of receipt, date of analysis, the analysis result, and the date the specimen was returned to the research center.
- 6. The slides will be shipped back to the hospital pathologist by courier for retention per hospital procedures.

5.8 90-Day Follow-Up (+/- 14 days)

- Assessment of symptoms and adverse events
- Using standard of care endoscopy, record the presence of persistent lesions. Determine % of tissue persistence of EndoRotor cases.
- Using standard of care endoscopy, record resection-associated stenosis.
- Assessment of the presence of post polypectomy syndrome.
- Independent quality assessment of pathology specimens by independent pathologist.

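### A second procedure is allowed at any time before the single 90-day visit and the start of the 90 days is not stated, so persistence and stenosis can be recorded as 90-day results well under 76 days after the last resection

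*Combined protocol and SAP*

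**What the plan says.** Section 5.7 provides that when removal is incomplete after one treatment visit, "a second visit can be scheduled to complete the removal in advance of the 90 day visit". Footnote 7 of Appendix 1, attached to the single Procedure column, repeats the permission: "Second procedure can be completed if complete resection was not achieved during initial procedure". Neither place gives a latest day, a minimum gap before follow-up or a restart of the clock. Neither names the device to be used.

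There is one follow-up visit. Section 3.2: "Study subjects shall return for clinic visits in 90 days (+/- 14 days) post-procedure". At that visit section 5.8 asks sites for two endoscopic findings: "Using standard of care endoscopy, record the presence of persistent lesions" and "Using standard of care endoscopy, record resection-associated stenosis". They supply secondary endpoint 3 ("Rate of persistence of disease at the location of resection at 90 days") and secondary endpoint 2 (stenosis).

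Section 8.2 admits a subject to the Per Protocol set on complete resection with the EndoRotor alone, no eligibility deviation and a completed 90-day visit. It sets no limit on the number of sessions and no minimum time since the last one.

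**The concern.** If the 90 days run from the index procedure, a subject who had a second session is examined sooner after the last resection than the label 90-day suggests, possibly by weeks or months. That subject is then pooled with subjects who had the full interval.

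The protocol itself explains why the interval matters. Section 1.3.1 cites a follow-up study in which scars that looked clear still held residual neoplasia (16 of 228, 7%) and late recurrences were found at 12 months. The first look in that study was at 3 to 6 months. Section 1.3.2 rests the timing of this study's visit on literature for a 3-month visit. A clear endoscopy a few weeks after a second session is weaker evidence than a clear endoscopy at three months, and stenosis has also had less time to appear.

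The subjects concerned are those whose lesion was not cleared the first time. The expected direction is therefore to understate persistence in the harder lesions, which favours the device.

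**Working it through.** **Inputs.** Visit window 90 +/- 14 days (3.2, 5.8, Appendix 1). Second procedure at any time before that visit (5.7, footnote 7). Enrollment to December 2019 and last follow-up by March 2020 (3.2). Final 90-day visit and closeout in a milestone dated June 2020 (Protocol Summary).

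**The plan's own window.** 90 - 14 = 76 and 90 + 14 = 104, so the visit falls on day 76 to 104.

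**Interval on the index clock.** With the visit on day v and the second session on day s, both counted from the index procedure, time from last resection to endoscopy = v - s.

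| Second session, s | Visit day 76 | Visit day 90 | Visit day 104 |
|---|---|---|---|
| 14 | 62 | 76 | 90 |
| 28 | 48 | 62 | 76 |
| 30 | 46 | 60 | 74 |
| 45 | 31 | 45 | 59 |
| 60 | 16 | 30 | 44 |
| 75 | 1 | 15 | 29 |

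The interval reaches the protocol's own minimum of 76 days only if s is at most v - 76. That is day 14 for a visit on day 90 and day 28 for the latest visit, day 104. After day 28 the interval is always under 76 days.

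**Which clock?** The passages side by side:

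- Section 5.7 speaks of the 90-day visit as an existing appointment that the second session must precede. This leans toward the index clock, although it could be read as fixing only the order of visits.
- Section 4.1 assesses SAEs "at index procedure and at 90 days, post-procedure". The pairing leans the same way.
- Section 3.2 counts from an unspecified procedure, and Appendix 1 treats a second procedure as part of the one Procedure column. Either clock fits.
- Calendar: 3.2 says "The last follow-up visit is expected to be completed by March 2020". For an index procedure on 31 December 2019, day 90 is 30 March 2020, which fits, but day 104 is 13 April 2020, which does not. March is therefore not a strict limit even on the index clock.
- The Protocol Summary's June 2020 milestone can hold a restarted clock. Day 75 after 31 December 2019 is 15 March 2020; 90 days later is 13 June and 104 days later is 27 June 2020.

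The index clock is the more natural reading, but the text does not settle it.

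**The case against.** The strongest reply is that the only demonstrable defect is an unstated clock start. Section 3.2 does not say that the days run from the index procedure, the calendar cannot decide the matter, and a site could properly count from the second procedure. This stands as far as it goes: a reader might infer that the plan prescribes short follow-up, and it does not. But it leaves the problem in place. On one reading the interval can be very short; if sites differ, two-session subjects are timed inconsistently and then pooled.

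Second, neither 5.7 nor footnote 7 says that the second session uses the EndoRotor. This also stands. A subject finished with another resection modality leaves the Per Protocol set, so the point concerns only those cleared with the EndoRotor alone.

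Third, a reader might infer that the primary endpoint is compromised. Technical Success as defined in 4.1 has no persistence component. Persistence enters the primary analysis only through the sentence in 8.4 that the analysis will be run on the percent of lesions with persistent disease, and that sentence does not match the defined endpoint. Otherwise the effect is on secondary endpoints that are summarised descriptively, with no test or success threshold.

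Fourth, late second sessions are permitted, not predicted. The follow-up endoscopy is standard of care, and nothing suggests that sites would plan it days after a resection. That is fair, and it is why no numerical bias is claimed.

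**Conclusion.** The point holds in a limited form. The plan allows a second procedure up to its only follow-up visit and does not say which procedure starts the 90 days. On the more natural, index-based reading, persistence and stenosis in a Per Protocol subject can be scored as 90-day results well under 76 days after the last resection, and always so when the second session is after day 28.

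This rests on two assumptions: that the clock is index-based, and that some subjects are cleared in two sessions with the EndoRotor alone. The understatement of persistence is an expected direction, argued from the protocol's own account of occult and late recurrence. Its size cannot be computed because the documents give neither the share nor the timing of second sessions. It should be corrected because the change is small and the interval cannot otherwise be seen in the results.

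**What to change.** **Main change.** In 3.2, 5.7 and Appendix 1, time the 90 +/- 14 day follow-up endoscopy from the last EndoRotor session for two-session subjects. Collect SAEs from the index procedure through that visit, so that both procedures are covered. Once the clock restarts, the sentence in 5.7 no longer bounds the second session, so give it a latest day. Day 75, the last day before the index-based window opens, would serve.

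**Data and reporting.** Record the date of each session. Report persistence, stenosis and technical success by number of sessions, with the interval from last session to endoscopy.

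**If the visit stays on the index clock.** Say so, and add a sensitivity analysis that excludes every assessment made under 76 days after the last session, positive and negative alike. Dropping only the early negatives would raise the rate by construction. For illustration, assume 9/60 persistent (15.0%, exact 95% half-width 0.0974) and 6 early assessments. If all 6 are negative, or if only negatives are removed, the result is 9/54 = 16.7% (half-width 0.1069). If one of the 6 is positive and all 6 are removed, it is 8/54 = 14.8% (half-width 0.1025). These counts are assumptions. The analysis would also lean toward single-session subjects, which should be stated beside it.

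**Cost.** One date field per session and a few lines of text. Two-session subjects have a later final visit and a longer SAE observation period. With a last index procedure on 31 December 2019 and a second session by day 75, the visit falls no later than 27 June 2020. That is within the June 2020 completion date but leaves only three days of that month for closeout, and the March 2020 expectation in 3.2 would need revising. The two-session group may be too small for more than counts.
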